2.8.4.3 Columbia-Suicide Severity Rating Scale (C-SSRS)

The number and percentage of subjects reporting any suicidal ideation or any suicidal behavior at baseline and any time post-baseline will be summarized descriptively by treatment group and all subjects. Refer to section 5.9 for details on scores.

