Subjects should be seen for all visits/assessments as outlined in the assessment schedule or as close to the designated day/time as possible. Missed or rescheduled visits should not lead to automatic discontinuation. Subjects who prematurely discontinue the study for any reason should be scheduled for a visit as soon as possible, at which time all of the assessments listed for the final visit will be performed. At this final visit, all dispensed investigational product should be reconciled, and the adverse event and concomitant medications recorded on the CRF.

Treatment discontinuation does not imply study discontinuation. Every effort should be attempted to ensure subjects complete the study visits event if treatment is discontinued.

If the **COVID-19 pandemic** limits or prevents on-site study visits, alternative methods of providing continuing care may be implemented. Phone calls, virtual contacts (e.g. teleconsult) or visits by site staff to the participant's home depending on local regulations and capabilities, can replace on-site study visits, for the duration of the pandemic until it is safe for the participant to visit the site again (see [Section 8.3](#) efficacy, [Section 8.4.1](#) Laboratory evaluations, [Section 8.4.3](#) Pregnancy, [Section 8.5.3](#) [REDACTED] and [Section 8.4](#) Safety monitoring.

Table 8-1 Assessment Schedule – Core Phase

Period	Screening			Open Label Randomized Treatment													
Visit Name	Screening	Baseline	Treatment	Week 4	Week 8	Week 12	Week 16	Week 20	Week 24	Week 28	Week 32	Week 36	Week 40	Week 44	Week 48	Week 52 / Early Exit ¹⁰	
Days	-42 to -28		-28 to -1		Day 1	28	56	84	112	140	168	196	224	252	280	308	364
Weeks	-6 to -4		-4 to -1		1	4	8	12	16	20	24	28	32	36	40	44	52
Informed consent	X																
Medical history/current medical conditions	X																
Demography	X																
Physical Examination ¹	X	X	X	X	X	X	X	X	X	X	X	X	X	X	X	X	X
Vital signs and body measurements	X	X	X	X	X	X	X	X	X	X	X	X	X	X	X	X	X
Electrocardiogram (ECG)	X									X							X
Pregnancy Test (serum) ²	X																X
Pregnancy test (urine) ²		X	X	X	X	X	X	X	X	X	X	X	X	X	X	X	X
Central blood chemistry - Erenumab	X		X							X							X
Central blood chemistry – SoC Oral Prophylactics ³	X		X	X ³	X ³	X ³	X ³	X ³	X	X ³							
Urine Drug Screen	X																
Columbia-Suicide Severity Rating Scale (C-SSRS) ⁴	X																
Randomization			X														
Study drug administration ⁵			X	X	X	X	X	X	X	X	X	X	X	X	X	X	X

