10.2.2 Prospective suicidality assessment

The Columbia-Suicide Severity Rating Scale (C-SSRS) is a questionnaire that prospectively assesses suicidal ideation and suicidal behavior. The C-SSRS will be administered at Screening.

A validated version of the C-SSRS will be used to capture self-reported C-SSRS data via an interactive voice response telephone system (eC-SSRS). The eC-SSRS uses a detailed branched logic algorithm to perform the C-SSRS subject interview, evaluating each subject's suicidality ideation and behavior in a consistent manner. At the conclusion of each assessment, the investigator will receive a detailed eC-SSRS Findings Report via e-mail or fax. If the system assesses the subject as having positive suicidal signs, the investigator will be immediately notified by either fax, email and/or via telephone.

If, at any time after screening and/or baseline, the score is "yes" on item 4 or item 5 of the suicidal ideation section of the C-SSRS or "yes" on any item of the suicidal behavior section, the subject must be referred to a mental health care professional for further assessment and/or treatment. The decision on whether the study treatment should be discontinued is to be taken by the investigator in consultation with the mental health professional to whom the subject is referred.

In addition, all life-threatening events must be reported as SAEs. For example, if a subject answers "yes" to one of the questions in the suicidal behavior section, an SAE must be reported if the event was life-threatening. All events of "Non-Suicidal Self-Injurious Behavior" (question also included in the suicidal behavior section) should be reported as AEs and assigned the appropriate severity grade.

11 Data Collection and Database management

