2.1 Data analysis general information

The final analysis will be performed by Novartis or a designated CRO. The current version of SAS or R software or later available versions will be used to perform all data analyses and to generate tables, figures and listings.

Data included in the analysis

The analysis cut-off date for the primary analysis of study data will be established after last subject completes or discontinues core phase that is when all subjects either complete week 52 on core phase or complete FU or discontinue early prior to week 52. All statistical analyses will be performed using all data collected in the database up to the data cutoff date. All data with an assessment date or event start date (e.g. vital sign assessment date or start date of an adverse event) prior to or on the cut-off date will be included in the analysis. Any data collected beyond the cut-off date will not be included in the analysis and will not be used for any derivations.

All events with start date before or on the cut-off date and end date after the cut-off date will be reported as ‘continuing at the cut-off date’. The same rule will be applied to events starting before or on the cut-off date and not having documented end date. This approach applies, in particular, to adverse event and concomitant medication reports. For these events, the end date will not be imputed and therefore will not appear in the listings.

General analysis conventions

Pooling of center: Unless specified otherwise, data from all study centers will be pooled for the analysis. Due to expected small size of centers, no center effect will be assessed.

Qualitative data (e.g., gender, race, etc.) will be summarized by means of contingency tables by treatment group; a missing category will be included as applicable. Percentages will be calculated using the number of subjects in the relevant population or subgroup as the denominator.

Quantitative data (e.g., age, body weight, etc.) will be summarized by appropriate descriptive statistics (i.e. mean, standard deviation, median, minimum, and maximum) by treatment group.

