2.1.1.4 Baseline

The baseline period for efficacy analysis is defined as the period between week -4 visit (when eDiary device is dispensed to the subject for daily data capture) and the day prior to study day 1 (study day 1 is not included).

A baseline for subject reported outcome (PRO) and safety (including Columbia-Suicide Severity Rating Scale (C-SSRS)) values refers to the last evaluable measurement prior to the first administration of the study drug, irrespective of re-screening. In this case, baseline values will be the value obtained on the day of the randomization (Day 1, Visit 101), or on an earlier visit (scheduled or unscheduled) which is the closest to Visit 101, if Visit 101 is missing or the assessment was not done at baseline.

Baseline weight and height are taken from vital signs screening visit.

eCSSRS is collected at screening or before randomisation and patients should complete “lifetime assessment eCSSRS questionnaire” at screening and if need arises during the course of the trial complete “since last contact eCSSRS questionnaire”. Hence, we do not have “Evaluation timeframe” (TMFRM) variable collected and baseline eCSSRS will correspond to the last evaluable measurement prior to the first administration of the study drug, irrespective of re-screening. For this analysis, each subject can only be counted once for each event. However, a subject can be counted in several different events.

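### The post-baseline C-SSRS percentage in SAP 2.8.4.3 cannot be read as an incidence or an arm comparison, because the scale is scheduled only at Screening and repeated only as needed

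*SAP*

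**What the plan says.** Protocol 10.2.2 gives the timing in one sentence: "The C-SSRS will be administered at Screening". Table 8-1 has a single mark in the C-SSRS row. The same protocol section sets a rule for later positive answers. If "at any time after screening and/or baseline, the score is" positive on ideation item 4 or 5, or on any behaviour item, "the subject must be referred to a mental health care professional for further assessment and/or treatment".

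SAP 2.1.1.4 says that subjects complete the lifetime questionnaire at screening and, "if need arises during the course of the trial complete" a since-last-contact version. It adds that no evaluation-timeframe variable is collected. SAP 2.1.1.6 includes the C-SSRS among the assessments mapped to the Week 4 to Week 52 visit windows.

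SAP 2.8.4.3 then specifies the output, for each arm and overall: "The number and percentage of subjects reporting any suicidal ideation or any suicidal behavior at baseline and any time post-baseline will be summarized descriptively". It names no denominator. The general rule in SAP 2.1 is "Percentages will be calculated using the number of subjects in the relevant population or subgroup as the denominator", and for qualitative data "a missing category will be included as applicable". SAP 2.8 bases safety analyses on randomized subjects with at least one dose and does not impute missing safety data.

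**The concern.** The planned table presumes post-baseline information on suicidality in both arms, but the schedule does not produce it. After Screening, a C-SSRS result exists only for a subject for whom someone judged a repeat necessary. Neither document says what prompts that judgement, and protocol 10.2.2 does not mention the as-needed form. Treatment is open to subjects, investigators and assessors (protocol 6.4), so the decision to ask can differ between arms for reasons unrelated to the true rate.

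At stake is a by-arm percentage in the study report that looks like a safety result and is largely a measure of who was questioned. The trial admits subjects with stable anxiety or major depressive disorder (exclusion criterion 10), so such a figure could be read as reassurance, or as a signal, without support for either.

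**Working it through.** The documents state no expected C-SSRS rate, so there is no figure to reproduce. The check sets schedule against analysis, then shows how far the percentage can move.

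**1. Schedule against output.** Post-baseline Core Phase visits run every four weeks from Week 4 to Week 52: 52 / 4 = 13 visits. C-SSRS scheduled at these visits: 0 of 13. Planned output: number and percentage with an event after baseline, by arm. The only source is the as-needed form in SAP 2.1.1.4. This SAP covers the Core Phase only, so the Extension Phase schedule does not alter this.

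**2. Denominator.** Reading SAP 2.1 with 2.8, the natural choice is the Safety Set. The text also allows a subgroup, such as those assessed, and a missing category. SAP 2.8.4.3 does not choose.

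**3. Illustration.** Let t be the true post-baseline rate, s the share of true cases given an as-needed C-SSRS, and f the share of non-cases given one. All three are assumptions.

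- Safety Set denominator, with unassessed subjects contributing no event: shown rate = t × s.
- Assessed-only denominator: shown rate = t × s / [t × s + (1 − t) × f].

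With f = 2%:

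| True rate t | s | Safety Set | Assessed only |
|---|---|---|---|
| 1% | 10% | 0.1% | 4.8% |
| 1% | 50% | 0.5% | 20.2% |
| 3% | 10% | 0.3% | 13.4% |
| 3% | 50% | 1.5% | 43.6% |
| 5% | 10% | 0.5% | 20.8% |
| 5% | 50% | 2.5% | 56.8% |

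Worked row (t = 3%, s = 50%): 0.03 × 0.50 = 0.015, or 1.5%. Over assessed subjects: 0.015 / (0.015 + 0.97 × 0.02) = 0.015 / 0.0344 = 43.6%.

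The Safety Set figure is a lower bound and equals t only if every case is assessed (s = 100%). The assessed-only figure exceeds t whenever s is greater than f, that is, whenever assessment is aimed at those who need it, which is its stated purpose.

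**4. Between arms.** Suppose t = 3% in both arms, with s = 10% in one and 50% in the other. Over the Safety Set the table shows 0.3% against 1.5%, a fivefold ratio with no true difference.

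**5. Baseline beside post-baseline.** The baseline figure comes from the lifetime form. Exclusion criterion 17 removes only ideation items 4 and 5 within 6 months and suicidal behaviour within 2 years, so older events and lower ideation items can still count at baseline. The later form covers only the time since last contact. The two columns have different recall windows as well as different ascertainment.

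**The case against.** Several points on the other side are sound.

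- A reader might infer that the table will show a falsely low rate, with every unquestioned subject counted as event-free. The documents do not say so. SAP 2.1 allows a subgroup denominator and a missing category, and SAP 2.8 rules out imputation. Too low follows under the Safety Set reading; an assessed-only reading errs the other way. What stands is that the SAP leaves this open and neither choice gives an incidence.
- A reader might infer that the referral rule in protocol 10.2.2 has nothing to act on. It is conditional on a score existing, and the as-needed form in SAP 2.1.1.4 can supply one. What stands is a gap in cross-reference: the protocol names no assessment after Screening.
- A reader might infer that the SAP plans a comparison with baseline. It does not: no change, shift or test is specified. What stands is that two figures on different recall windows are to be summarised together with no caution.
- The Screening C-SSRS serves eligibility (exclusion criterion 17), current evidence of depression is excluded, and the scale supports no study objective. This limits the importance of the point.
- Adverse events are sought at every visit (protocol 10.1.1), life-threatening suicidal events must be reported as SAEs, and protocol 12.5.2 already plans adverse event summaries by SMQ. Suicidality is therefore not monitored by the C-SSRS table alone. These routes rest on non-directive questioning and do not make the C-SSRS percentage interpretable.

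**Conclusion.** The point holds, as a minor one. Following SAP 2.8.4.3 as written yields a post-baseline percentage that cannot be interpreted as an incidence or as a between-arm comparison, and that should not be set against the lifetime baseline figure. This rests on the texts alone: Screening-only scheduling, an undefined need-based repeat, open-label conduct, and no stated denominator for the table.

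The size cannot be determined from the documents. Under the assumed inputs, a true 3% could appear as anything from 0.3% (Safety Set, 10% of cases assessed) to 43.6% (assessed only, 50% of cases and 2% of non-cases assessed). These figures show sensitivity to unstated choices and do not predict this trial's result. One descriptive safety table is affected; no efficacy analysis is.

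**What to change.** In SAP 2.8.4.3:

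- Remove the post-baseline percentage.
- Report, per arm, the number of subjects with any post-baseline C-SSRS, and list their results with date and form version.
- State that lifetime and since-last-contact results are not compared.

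Optionally, name the suicide/self-injury SMQ among the SMQ-based adverse event summaries that protocol 12.5.2 already plans; SAP 2.8.1 currently names SMQ summaries only for COVID-19 and hypertension. State that it is less sensitive than a scheduled questionnaire.

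Reconcile protocol 10.2.2 and Table 8-1 (Screening only, with a referral rule for any later positive score) with SAP 2.1.1.4, 2.1.1.6 and 2.8.4.3 (as-needed form, visit windows, post-baseline summary). Whether and when the scale is repeated is a clinical decision for the sponsor.

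The cost is a few lines of SAP text, one count and one listing, plus one SMQ table if the option is taken, all from data already collected, and the wording needed to align the two documents. What is lost is a percentage that could not have been interpreted.

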2.9 Pharmacokinetic endpoints

Not Applicable.

2.10 PD and PK/PD analyses

Not Applicable.

2.11 Patient-reported outcomes (PRO)

PRO based on PGIC score is a secondary endpoint and it is detailed in [section 2.7](#). 

2.12 Biomarkers

Not Applicable.

2.14 Interim analysis

Not Applicable.

3 Sample size calculation

The sample size calculation is based on the primary variable, rate of net benefit. The details of hypothesis testing are described in [section 2.5.2](#).

A 2-sided test with significance level 0.05, and a 2:1 randomization ratio are considered. A sample size of 591 (394 erenumab arm; 197 control arm) is required to achieve 90% power to reject the odds ratio of 1 set by the null hypothesis when the odds ratio is actually 2, and success rate in control arm is 0.18.

An odds ratio of 2 and control rate of 0.18 is based on more conservative assumptions for rate of net benefit than observed previously (for erenumab in studies NCT02456740, NCT01952574, and oral cycling in Hepp et al 2017, Shei et al 2015), resulting in a rate difference of 12%. Sample size calculations were done using PASS 11 and Cochran-Mantel-Haenszel test was used.

4 Change to protocol specified analyses

Not applicable.

5 Appendix

5.1 Imputation rules

Subjects may miss specific data points for a variety of causes. In general, data could be missing due to a subject's early withdrawal from study, a missed visit, or inability to evaluate an endpoint at a particular point in time. For this study, most of the efficacy endpoint will be collected via eDiary and subjects could miss entering several days of data in each 28-consecutive day interval. The general procedures outlined below describe what will be done when a data point is missing.

5.1.1 AE / Concomitant medication date imputation

Missing or incomplete dates will be listed as it is in any listings.

Incomplete start date of an adverse event or concomitant medication taken will be handled by following rule:

Table 5-1 Imputation of AE/Concomitant dates

	Missing	Imputation	Exception
Start date (AE, concomitant medication)	Day	01	Default to Study Day 1 if an adverse event starts the same year and month as Study Day 1 and the flag indicates that the adverse event started on or after the first dose on the Adverse Events eCRF
	Day/Month	01Jan	Default to Study Day 1 if an event started the same year as Study Day 1 and the flag indicates that the adverse event started on or after the first dose on the Adverse Events eCRF

	Day/Month/Year	No imputation	

5.1.2 Prior therapies date imputation

For prior medications with a stop date prior to the treatment phase (not possible to be at or after first drug administration), the start date will be imputed as the earliest possible start date and the stop date as the latest possible stop date:

For a missing/incomplete start date the minimum of the following will be imputed:

- The maximum of the earliest possible start date and the imputed birth date;
- The latest possible start date;
- The latest possible stop date.

For a missing/incomplete stop date the maximum of the following will be imputed:

- The minimum of the latest possible stop date and the date of first drug administration -1;
- The earliest possible stop date;
- The earliest possible start date.

Here, the earliest (latest) possible date is defined as:

- The date itself if it is complete;
- The date of the first (last) day of the month, if month and year are available but day is missing;
- The date of the first (last) day of the year, if year is available but day and month are missing;
- A very early (late) date, e.g., 01JAN1000 00:00hrs (01JAN3000 23:59hrs), if the date is completely missing.

5.1.3 Post therapies date imputation

NA.

5.1.4 Other imputations

5.1.4.1 eDiary data

The eDiary includes the following clinical outcome assessments:

- Incidence of headache (ie, migraine with or without aura or non-migraine headache)
- Time of onset of headache
- Time of resolution of headache
- Pain severity per headache

- Symptoms (eg, nausea, vomiting, photophobia, phonophobia)
- Presence of aura
- Use of acute medication during aura or to treat headache

as well as, patient-reported outcomes (PROs) measures.

Missing eDiary data in the calculation of monthly measurements about subjects' migraine and non-migraine headaches will be handled using the following method:

1. For monthly intervals with ≥ 14 days of eDiary days (including retrospective eDiary days) in each interval:

a) Monthly frequency measurements (including migraine days, headache days, migraine attacks, [REDACTED]) will be prorated to 28-day equivalents. Prorated result does not need to be rounded.

[REDACTED]

2. For monthly intervals with < 14 days of eDiary use (including retrospective eDiary days), all monthly measurement will be set as missing and will be handled as described in [Section 5.1.5.3](#).

Table 5-2 Rules for handling missing and incomplete eDiary data

Monthly Endpoint	Condition	Proration Method (does not need to be rounded)
Monthly frequency measurements (including migraine days, headache days, migraine attacks, hours of migraine headaches, [REDACTED] [REDACTED])	If diary days in entire baseline or interval post baseline ≥ 14 (including retrospective eDiary days), then do proration; Else monthly measurement is set to missing [diary days is a day with all headache related questions completed retrospectively or not]	Number of observed migraine days * 28/ Number of information days in interval [information day is a diary day or headache day]

Missing PROs scheduled to be collected at office visit at certain assessment will not be imputed.

5.1.4.2 Missing Baseline Evaluation

Missing baseline evaluations will not be imputed.

All subjects included in the full analysis set will have baseline monthly rate or monthly average of migraine and non-migraine headaches related measurements after applying proration rule defined in [Section 5.1.5.1](#) since only subject with $\geq 80\%$ compliance of eDiary use during baseline will be eligible for randomization.

5.1.4.3 Missing Post-baseline Evaluation

Primary analysis will be conducted using the stratified CMH test on observed data without imputation (see [Section 5.5.1](#)).

In the sensitivity analysis on primary and secondary efficacy endpoints, missing continuous efficacy endpoints will be handled using multiple imputation (MI) with assumption of missing at random (MAR). See below for more details.

To address the impact of missing data on primary efficacy analysis, the amount of missing data, the distribution of missing data among treatment groups, and the reasons for missing data will be examined.

If the proportion of missing data in primary endpoint is high (e.g., $> 20\%$ for primary analysis at week 52) or if substantial imbalance occurs amongst the treatment groups, further analysis will be performed to

- examine the frequency and reason of missing data
- determine if there are any patterns in the missing data
- distinguish true missing values from other unknown values (e.g., due to measurement or sample processing error)

Additional sensitivity analyses, including those based on alternative missing data assumptions, will be performed as deemed appropriate and necessary.

5.1.4.3.1 Multiple Imputation (MI) and MCMC Method

The multiple imputation assume that the missing data are missing at random (MAR), that is, the probability that an observation is missing may depend on the observed values but not the missing values. It also assumes that the parameters q of the data model and the parameters f of

the missing data indicators are distinct. That is, knowing the values of q does not provide any additional information about f , and vice versa. If both MAR and the distinctness assumptions are satisfied, the missing data mechanism is said to be ignorable. The MI procedure provides three methods for imputing missing values and the method of choice depends on the type of missing data pattern. For monotone missing data patterns, either a parametric regression method that assumes multivariate normality or a nonparametric method that uses propensity scores is appropriate. For an arbitrary missing data pattern, a Markov chain Monte Carlo (MCMC) method that assumes multivariate normality can be used.

In MCMC, one constructs a Markov chain long enough for the distribution of the elements to stabilize to a common, stationary distribution. By repeatedly simulating steps of the chain, it simulates draws from the distribution of interest.

In Bayesian inference, information about unknown parameters is expressed in the form of a posterior distribution. MCMC has been applied as a method for exploring posterior distributions in Bayesian inference. That is, through MCMC, one can simulate the entire joint distribution of the unknown quantities and obtain simulation-based estimates of posterior parameters that are of interest.

Assuming that the data are from a multivariate normal distribution, data augmentation is applied to Bayesian inference with missing data by repeating a series of imputation and posterior steps. These two steps are iterated long enough for the results to be reliable for a multiply imputed data set (Schafer 1997). The goal is to have the iterations converge to their stationary distribution and then to simulate an approximately independent draw of the missing values.

Sample SAS code for MI using MCMC method will be provided as instruction to TFLs. Further, as a sensitivity analysis, the pattern-mixture model approach is used to model the distribution of a response as the mixture of a distribution of the observed responses and a distribution of the missing responses, for which the missing values can be imputed under a plausible scenario for which the missing data are missing not at random. The control-based pattern imputation, in which, the set of observations from control group are used to derive the imputation model.

